3.2. Secondary Endpoint(s)

Sentinel Cohort:

- RSV A– and RSV B–neutralizing antibody titers measured before Vaccination 1 and 2 weeks and 1, 2, 3, and 6 months after Vaccination 1.

Expanded Cohort:

- RSV A– and RSV B–neutralizing antibody titers measured before Vaccination 1 and 1, 2, 3, and 6 months after Vaccination 1.
- Hemagglutination inhibition assay (HAI) titers for all strains in the SIIV measured before and 1 month after SIIV administration.

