3.2.1. RSV A– and RSV B–Neutralizing Antibody Titers

RSV A– and RSV B–neutralizing antibody titers will be determined on all sera collected at applicable visits for antibody testing.

Titers above the lower limit of quantitation (LLOQ) are considered accurate and their quantitated values will be reported. Refer to Section 5.3.2 for LLOQs. Titers below the corresponding LLOQ or denoted as below the limit of quantitation (BLQ) will be set to $0.5 \times \text{LLOQ}$ for analysis. Missing assay results will not be imputed.

In addition to titer, the neutralizing titer (NT) fold rise from before vaccination to each time point after the vaccination will be derived for both RSV A and RSV B as detailed below:

1. For the sentinel cohort: NT fold rise will be derived from before Vaccination 1 to each time point after Vaccination 1 with NT assay performed (2 weeks and 1, 2, 3, 6, and 12 months after Vaccination 1).
2. For the expanded cohort: NT fold rise will be derived from before Vaccination 1 to each time point after Vaccination 1 with NT assay performed (1, 2, 3, 6, and 12 months after Vaccination 1).

CCI

For calculating a fold rise, $< \text{LLOQ}$ will be converted to $\frac{1}{2} \text{LLOQ}$ for a numerator, and $< \text{LLOQ}$ will be converted to LLOQ for a denominator when only one of either the numerator or denominator is $< \text{LLOQ}$. If both the numerator and denominator are $< \text{LLOQ}$, then both will be converted in the same way.

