4.2.1. Evaluable RSV Immunogenicity Population

This evaluable immunogenicity population will include subjects from the expanded cohort who:

- Are eligible (have signed informed consent and met all inclusion/not met any exclusion criteria) and were randomized into the study;
- Have received the vaccine (RSV vaccine or placebo) at Visit 1 as randomized;
- Have a Visit 2 (1 month after Vaccination 1) blood draw for assay testing within 27 to 42 days after Visit 1, inclusive, after vaccine administration (note: the 27- to 42-day interval is calculated as the Visit 2 date minus the Visit 1 date);
- Have at least 1 valid and determinate assay result for the 1-month postvaccination visit;
- Have no major protocol violation as determined by the study clinician.

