5.2.2.2. Geometric Mean Fold Rise

Geometric mean fold rises (GMFRs) will be limited to subjects with nonmissing values at both visits. Individual subject antibody levels fold rise from one time point to another time point will be transformed in natural logarithm scale for analysis. Means and their 95% CIs on the natural log scale will be based on the 1-sample Student's t distribution. GMFRs and corresponding 95% CIs will be calculated by exponentiating the results from the natural log scale.

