5.2.2.3. Geometric Mean Ratio

The geometric mean ratio (GMR) will be calculated by transforming the group mean difference of the antibody levels in natural logarithm scale to original scale. 95% CI is also computed by exponentiating the CIs from the natural log scales using 2-sample Student's t distribution for the mean difference of measures on the logarithmically transformed assay results.

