5.2.2.5. Assessing Interference

To understand whether concomitant administration of influenza and RSV vaccines in the expanded cohort interferes with the immune response to RSV vaccine, the GMR with associated 95% CI for RSV A- and RSV B-neutralizing antibody titers between sera drawn from subjects vaccinated with RSV vaccine with or without concomitant SIIV at 1 month after Vaccination 1 will be calculated.

Using RSV vaccine 60 µg as an example, the GMR will be calculated as follows:

- Numerator: RSV vaccine 60 µg/SIIV+placebo; and denominator: RSV vaccine 60 µg/placebo+SIIV.
- Numerator: RSV vaccine 60 µg+Al(OH)₃/SIIV+placebo; and denominator: RSV vaccine 60 µg+Al(OH)₃/placebo+SIIV.

To understand whether concomitant administration of influenza and RSV vaccines in the expanded cohort interferes with the immune response to SIV vaccine, the GMR with associated 95% CI for HAI for strains in SIV by comparing sera drawn from subjects vaccinated with SIV concomitantly with RSV vaccine at 1 month after Vaccination 1 or with SIV alone at 1 month after Vaccination 2 will be calculated.

- Numerator: RSV vaccine 60 µg/SIV+placebo; and denominator: placebo/placebo+SIV.
- Numerator: RSV vaccine 60 µg+Al(OH)₃/SIV+placebo, and denominator: placebo/placebo+SIV.
- Numerator: RSV vaccine 60 µg/SIV+placebo; and denominator: RSV vaccine 60 µg/placebo + SIV.
- Numerator: RSV vaccine 60 µg+Al(OH)₃/SIV+placebo; and denominator: RSV vaccine 60 µg+Al(OH)₃/placebo + SIV.

Similar combinations and comparisons will be done for the RSV vaccine 120-µg and 240-µg dose levels.

CCI

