5.3.2. Immunogenicity Data

Any assays above LLOQ are considered accurate and their quantitated values will be reported. Values below the LLOQ or denoted as BLQ will be set to $0.5 \times \text{LLOQ}$ for analysis.

For calculating a fold rise, < LLOQ will be converted to $0.5 \times \text{LLOQ}$ for a numerator, and < LLOQ will be converted to LLOQ for a denominator when only one of either the numerator or denominator is < LLOQ. If both the numerator and denominator are < LLOQ, then both will be converted in the same way.

The LLOQs for each assay are listed in Table 10.

Table 10. LLOQ Titers for All Assay

Serotype	LLOQ
NT RSV A-50%	50
NT RSV B-50%	70
CCI	
	0.55
HAI: A CCI	10
HAI: A CCI	10
HAI: B	10
CCI	

Abbreviations: HAI = hemagglutination inhibition assay; CCI
 LLOQ = lower limit of quantification; NT = neutralizing titer; G; CCI

Values for sera that are insufficient (QNS), indeterminate results, or values recorded as “not done” will be set to “missing.” Additionally, any time point with no blood draws will not be included in the analysis. No imputation will be done for these missing values.

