6.2.1.2. Additional Summary

For the sentinel cohort, expanded cohort, and combined sentinel and expanded cohorts, GMTs at all other applicable visits after Vaccination 1 will be summarized along with associated 95% CIs for each vaccine group, by age stratum, for both RSV A– and RSV B–

neutralizing antibody titers. Additionally, all fold rises specified in Section 3.2.1 will be summarized with GMFRs and associated 95% CIs.

The following comparisons will be made in order to assess the interference of SIIV coadministration with the immune response induced by RSVpreF among the expanded cohort:

- GMTs for RSV A NT and RSV B NT will be compared between the RSVpreF with SIIV group and the RSVpreF-only (or SIIV after RSVpreF) group for each dose/formulation, by age stratum. GMRs and associated 95% CIs will be calculated from 1 month through 12 months after Vaccination 1.

Figures:

For the combined sentinel and expanded cohorts, NT GMT kinetics for each vaccine group will be plotted across all visits, by age stratum.

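### The RSV A/B interference GMRs use a valid but unadjusted two-sample t interval, although the titer before Vaccination 1 is already measured and could narrow it

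*SAP*

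**What the plan says.** Section 5.2.2.3 gives the only visible GMR method. The difference in group means is taken on the natural log scale, with an interval from the two-sample Student's t "distribution for the mean difference of measures on the logarithmically transformed assay results", and the result is exponentiated. No covariate is named.

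Section 5.2.2.5 uses the GMR to assess RSV interference "between sera drawn from subjects vaccinated with RSV vaccine with or without concomitant SIIV at 1 month after Vaccination 1". Section 6.2.1.2 repeats the comparison for each dose/formulation and age stratum and extends it: "GMRs and associated 95% CIs will be calculated from 1 month through 12 months after Vaccination 1".

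The baseline value is in hand. Section 3.2 lists expanded-cohort RSV A and B "neutralizing antibody titers measured before Vaccination 1 and 1, 2, 3, and 6 months after Vaccination 1". Section 3.2.1 derives each subject's fold rise from that sample at every later time point with "NT assay performed (1, 2, 3, 6, and 12 months after Vaccination 1"). Section 5.2.2.2 summarizes these paired data as geometric mean fold rises (GMFRs), which "will be limited to subjects with nonmissing values at both visits". The GMFRs are one-sample summaries by group. No visible text turns them into a baseline-adjusted ratio between groups.

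**The concern.** Sections 5.1.1 and 5.1.2 rule out hypothesis tests and decision rules, so the estimate and its interval are the whole result of the interference assessment. The width of the interval decides how much each GMR can say about whether SIIV alters the RSV response. With 39 subjects per arm in each age stratum before exclusions, that width is considerable.

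Part of the variation in a post-vaccination titer may reflect the level the subject started from. If it does, the unadjusted comparison leaves that part in the error term. It also lets a chance baseline difference between the two arms carry through to the GMR. Both can be reduced with a measurement already in the database.

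The rule reaches 6 dose/formulations × 2 age strata × 2 RSV subgroups = 24 GMRs at 1 month, and 24 × 5 time points (1, 2, 3, 6 and 12 months) = 120 in all.

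**Working it through.** The SAP states no precision or power for these GMRs, so there is no figure to reproduce.

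**Inputs from the SAP**
- Arm size (Section 2.2): 1014 subjects in 13 equal groups and 2 equal age groups, so 1014/13/2 = 39 per arm per age stratum.
- Confidence level (Section 5.2): two-sided 95%.

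**Assumed inputs (not in the SAP)**
- ln-titer SD: 0.9, range 0.7 to 1.1.
- Correlation ρ between ln titer before vaccination and after: 0 to 0.7. It may differ across the 1- to 12-month visits.
- 30 per arm as an illustration of size after exclusions.

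**Unadjusted log half-width**

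t(0.975, 2n−2) × SD × √(2/n). At n = 39 and SD 0.9: 1.9917 × 0.9 × √(2/39) = 0.406, a factor of 1.50. For SD 0.7 and 1.1 the factors are 1.37 and 1.64.

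**Expected ANCOVA log half-width**

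t(0.975, 2n−3) × SD × √(1−ρ²) × √[(2/n)(1 + 1/(2n−4))]. The last term is the average cost of estimating the slope. At n = 39, SD 0.9 and ρ = 0.5: 1.9921 × 0.9 × 0.8660 × √[(2/39)(1 + 1/74)] = 0.354, a factor of 1.425.

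| ρ | CI factor, n = 39, SD 0.9 | Width change, n = 39 | Width change, n = 30 |
|---|---|---|---|
| 0 | 1.505 | +0.7% | +0.9% |
| 0.1 | 1.502 | +0.2% | +0.4% |
| 0.2 | 1.493 | −1.3% | −1.1% |
| 0.3 | 1.477 | −3.9% | −3.7% |
| 0.5 | 1.425 | −12.8% | −12.6% |
| 0.7 | 1.339 | −28.1% | −27.9% |

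The percentages do not depend on the SD. Break-even is at ρ = 0.117 (n = 39) or 0.135 (n = 30). To match the ANCOVA width at n = 39, an unadjusted analysis would need 43, 51 or 75 per arm at ρ = 0.3, 0.5 or 0.7.

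**Chance baseline imbalance.** The table shows expected values. If the arms happen to differ at baseline by 2 standard errors, replace 1 + 1/(2n−4) by 1 + 4/(2n−2). The width change at ρ = 0, 0.3, 0.5 and 0.7 becomes +2.6%, −2.1%, −11.1% and −26.7% at n = 39, and +3.4%, −1.3%, −10.4% and −26.1% at n = 30. The same imbalance also moves the unadjusted estimate. With equal pre and post SDs of 0.9 and ρ = 0.5, 2 SE is 2 × 0.9 × √(2/39) = 0.408, which shifts the GMR by a factor of exp(0.5 × 0.408) = 1.23.

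**Coverage and values below the LLOQ.** In simulations of 20,000 datasets per setting (n = 39 and 30; 0%, 10% or 25% of baselines below the LLOQ and set to half of it), coverage was 0.948–0.954 unadjusted and 0.948–0.953 with ANCOVA. With 25% below the LLOQ at n = 39, the width changes were −3.7%, −11.9% and −26.0% at ρ = 0.3, 0.5 and 0.7.

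**The case against.** The strongest reply is that nothing here is wrong. A two-sample t interval between randomized arms is conventional, fully specified and consistent with the t-based GMTs and GMFRs. That stands, and the point is one of efficiency only.

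The size of the gain is also unknown. The document does not locate ρ, ANCOVA is expected to be slightly wider below about 0.12, and at ρ = 0.3 the factor moves only from 1.50 to 1.48, which would change few readings. This stands too. What favours the change is the asymmetry: an expected loss under 1% if baseline is uninformative, against 13% to 28% narrower intervals at ρ of 0.5 to 0.7.

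The analyses are descriptive, have no margin, and sit under an additional summary. However, Section 7 says expanded-cohort results will be used to select doses and formulations, and an imprecise descriptive ratio tells the reader less.

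Baseline GMTs and GMFRs are shown by group, so a reader can see an imbalance but gets no adjusted ratio with its interval.

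From 2 months on, the comparator arm has itself received SIIV at Visit 2. Those 96 ratios therefore compare concomitant with sequential SIIV, not SIIV with none. This affects how they are read, but not whether baseline adjustment is sound. The 24 ratios at 1 month are the direct interference comparison.

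Finally, redacted text follows Section 5.2.2.5, so an adjusted model elsewhere cannot be excluded. The finding rests on the visible text.

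**Conclusion.** The concern holds as a recommended improvement in precision. The plan's interval is valid, but it leaves unused a covariate that is measured before any randomized injection and already paired with each later titer.

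For any ρ above about 0.12 the adjusted interval is expected to be narrower, by about 4% at 0.3, 13% at 0.5 and 28% at 0.7. Below that the expected cost is at most 0.7% at 39 per arm or 0.9% at 30, and more if the arms happen to be imbalanced at baseline. The percentages rest on the assumed ρ, and the CI factors also on the assumed SD.

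The conclusion is limited to the RSV GMRs. HAI is specified before and 1 month after SIIV, so in the sequential groups the pre-SIIV sample is Visit 2, after the randomized RSV vaccine or placebo, with Visit 1 only as a fallback (Section 3.2.2). That value is not a clean baseline for adjustment.

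**What to change.** In Sections 5.2.2.3, 5.2.2.5 and 6.2.1.2, specify for the RSV A/B interference GMRs only:
- At each time point, an ANCOVA of ln titer on vaccine group and ln titer before Vaccination 1, fitted for each dose/formulation pair within age stratum. The GMR and 95% CI come from the exponentiated group difference.
- For the covariate, the titer rule in Section 5.3.2 ("Values below the LLOQ or denoted as BLQ will be set to" half the LLOQ), and not the separate fold-rise convention for denominators in the same section.
- The unadjusted GMR kept as supportive.
- HAI GMRs left unadjusted unless Visit 1 HAI results already exist in all groups.

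The cost is one model statement and a little programming, plus a second column of RSV ratios. No samples or assays are added. The evaluable population in Section 4.2.1 asks only that subjects "Have at least 1 valid and determinate assay result for the 1-month postvaccination visit", so those without a baseline titer drop out of the adjusted GMR, as they already do from the GMFR. The supportive unadjusted GMR keeps them, and the SAP should say so.

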5.2.2.4. Reverse Cumulative Distribution Curves

Empirical reverse cumulative distribution curves (RCDCs) will plot the proportion of subjects with values equal to or exceeding a specified assay value versus the indicated assay value, for all observed assay values. Data points will be joined by a step function with the data point on the left side of the step.

5.2.2.5. Assessing Interference

To understand whether concomitant administration of influenza and RSV vaccines in the expanded cohort interferes with the immune response to RSV vaccine, the GMR with associated 95% CI for RSV A- and RSV B-neutralizing antibody titers between sera drawn from subjects vaccinated with RSV vaccine with or without concomitant SIIV at 1 month after Vaccination 1 will be calculated.

Using RSV vaccine 60 µg as an example, the GMR will be calculated as follows:

- Numerator: RSV vaccine 60 µg/SIIV+placebo; and denominator: RSV vaccine 60 µg/placebo+SIIV.
- Numerator: RSV vaccine 60 µg+Al(OH)₃/SIIV+placebo; and denominator: RSV vaccine 60 µg+Al(OH)₃/placebo+SIIV.

To understand whether concomitant administration of influenza and RSV vaccines in the expanded cohort interferes with the immune response to SIV vaccine, the GMR with associated 95% CI for HAI for strains in SIV by comparing sera drawn from subjects vaccinated with SIV concomitantly with RSV vaccine at 1 month after Vaccination 1 or with SIV alone at 1 month after Vaccination 2 will be calculated.

- Numerator: RSV vaccine 60 µg/SIV+placebo; and denominator: placebo/placebo+SIV.
- Numerator: RSV vaccine 60 µg+Al(OH)₃/SIV+placebo, and denominator: placebo/placebo+SIV.
- Numerator: RSV vaccine 60 µg/SIV+placebo; and denominator: RSV vaccine 60 µg/placebo + SIV.
- Numerator: RSV vaccine 60 µg+Al(OH)₃/SIV+placebo; and denominator: RSV vaccine 60 µg+Al(OH)₃/placebo + SIV.

Similar combinations and comparisons will be done for the RSV vaccine 120-µg and 240-µg dose levels.

CCI

5.3. Methods to Manage Missing Data

5.3.1. Safety Data

Standard algorithms on handling missing AE dates and missing AE severity will be applied as described in the safety rulebook summary.

Missing data handling rules on the safety data are described in detail in the corresponding endpoint sections.

5.3.1.1. Reactogenicity Data

For derived variables based on reactogenicity data, if any day of the 14-day e-diary is available, the “any day (Days 1-14)” data will be considered as nonmissing.

The reactogenicity data are collected through the e-diary, which does not allow subjects to skip the question. Therefore, for a specific day, if the e-diary data are transferred for that day, all of the reactogenicity data for the subject on that day are nonmissing. No missing reactogenicity data will be imputed other than what is described in Section 3.1.

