3.1.1.1. Presence of Local Reactions

For the summary of the presence (yes or no) of a local reaction during the interval from Day 1 through Day 14 after Vaccination 1 [REDACTED] where Day 1 is the day of vaccination, the following 2 variables are required in order to compute the proportions:

1. Presence (yes or no) of each local reaction on any day (Day 1 through Day 14).

The derivation is described in Table 2.

Table 2. Derived Variables for Each Local Reaction

Variable ^a	Yes (1)	No (0)	Missing (.)
Any day (Days 1-14)	Subject reports the reaction as “yes” on any day (Days 1-14).	Subject reports the reaction as “no” on all 14 days or as a combination of “no” and “missing” on all 14 days.	Subject reports the reaction as “missing” on all 14 days.

a. The variable will be defined for each of the 3 local reactions.

2. Presence (yes or no) of any local reaction on any day (Day 1 through Day 14);

For any local reaction on any day, a similar definition can be applied as given in Table 3.

Table 3. Derived Variables for Any Local Reaction

Variable	Yes (1)	No (0)	Missing (.)
Any day (Days 1-14)	Subject reports any local reaction as “yes” on any day (Days 1-14).	Subject reports the reaction as “no” on all 14 days or as a combination of “no” and “missing” on all 14 days for all 3 local reactions.	Subject reports all local reactions as “missing” on all 14 days.

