3.1.1.2. Maximum Severity of Local Reactions

The grading of local reactions is listed in Table 4.

Table 4. Grading Scale for Local Reactions

	Mild Grade 1	Moderate Grade 2	Severe Grade 3	Grade 4^a
Redness	2.5 cm to 5.0 cm (5 to 10 measuring device units)	>5.0 cm to 10.0 cm (11 to 20 measuring device units)	>10 cm (>20 measuring device units)	Necrosis or exfoliative dermatitis
Swelling	2.5 cm to 5.0 cm (5 to 10 measuring device units)	>5.0 cm to 10.0 cm (11 to 20 measuring device units)	>10 cm (>20 measuring device units)	Necrosis
Pain (at the injection site)	Does not interfere with activity	Interferes with activity	Prevents daily activity	Emergency room visit or hospitalization for severe pain at the injection site

- a. Grade 4 assessment should be made by the investigator using the AE severity grading scale. The assessment will be collected on the AE case report form and thus not reported from the e-diary.

The following 2 variables are required in order to compute the proportions of subjects reporting maximum severity.

1. Maximum severity of each local reaction on any day (Day 1 through Day 14).

The maximum severity (highest grading) of each local reaction within 14 days after vaccination will be derived. The maximum severity will be derived as follows:

- = “Missing,” if values are missing for all days (Days 1-14);
- = 0, if the subject reports all reactions as “no” or a combination of “missing” and “no” for all days (Days 1-14);
- = Highest grade (maximum severity) within 14 days after vaccination, if the answer is not “no” for at least 1 day.

2. Maximum severity of any local reaction on any day (Day 1 through Day 14).

The maximum severity for any local reaction will be derived as follows:

- = “Missing,” if values are missing for all days (Days 1-14) across all 3 local reactions;
- = 0, if the subject reports all reactions as “no” or a combination of “missing” and “no” for all days (Days 1-14) for any individual local reaction;
- = Highest grade (maximum severity) within 14 days after vaccination, if the answer is not “no” for at least 1 day for at least 1 local reaction.

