3.1.2. Systemic Events

Systemic events, including fever, fatigue, headache, vomiting, nausea, diarrhea, muscle pain, and joint pain, are reported via e-diary from Day 1 through Day 14 after Vaccination 1 [redacted] where Day 1 is the day of vaccination with RSV vaccine or placebo (Visit 1 for the sentinel/expanded cohort; [redacted]). The derivations below for systemic events will be handled similarly to the way local reactions are handled for presence, severity level, duration, onset day, and severe systemic events on each day.

1. Presence (yes or no) of each systemic event on any day (Day 1 through Day 14);

2. Presence (yes or no) of any systemic event on any day (Day 1 through Day 14);
3. Maximum severity of each systemic event on any day (Day 1 through Day 14);
4. Maximum severity of any systemic event on any day (Day 1 through Day 14);
5. Duration of each systemic event;
6. Onset day of each systemic event;
7. Presence (yes or no) of any severe systemic event on each of the 14 days.

The systemic events gradings are provided in Table 6.

Table 6. Grading Scale for Systemic Events

	Mild Grade 1	Moderate Grade 2	Severe Grade 3	Grade 4^a
Fatigue (= tiredness in diaries)	Does not interfere with activity	Some interference with activity	Prevents daily routine activity	Emergency room visit or hospitalization for severe fatigue
Headache	Does not interfere with activity	Some interference with activity	Prevents daily routine activity	Emergency room visit or hospitalization for severe headache
Vomiting	1 to 2 times in 24 hours	>2 times in 24 hours	Requires intravenous hydration	Emergency room visit or hospitalization for severe vomiting
Nausea	Does not interfere with activity	Some interference with activity	Prevents daily routine activity	Emergency room visit or hospitalization for severe nausea
Diarrhea	2 to 3 loose stools in 24 hours	4 to 5 loose stools in 24 hours	6 or more loose stools in 24 hours	Emergency room visit or hospitalization for severe diarrhea
Muscle pain	Does not interfere with activity	Some interference with activity	Prevents daily routine activity	Emergency room visit or hospitalization for severe muscle pain
Joint pain	Does not interfere with activity	Some interference with activity	Prevents daily routine activity	Emergency room visit or hospitalization for severe joint pain

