6.6.2.1. E-Diary Completion

For each cohort, the number and percentage of vaccinated subjects with e-diary data transmitted for each day (Days 1 through 14) and for all days after Vaccination 1 and Vaccination 2 in the required reporting period may be summarized by vaccine group and for all subjects included in the safety population.

However, the e-diary transmission rate is relevant to monitoring study conduct. The summary may be omitted, as the information is included in reactogenicity listings.

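### Untransmitted e-diary days are scored as no reaction, so the primary reactogenicity rates can be understated, and the any-day n and N do not show how many *no* subjects had incomplete diaries

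*SAP*

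**What the plan says.** Four parts of the SAP fix the rule, and they agree.

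- **Section 3.1.1.1, Table 2.** A local reaction is scored *no* when: "Subject reports the reaction as “no” on all 14 days or as a combination of “no” and “missing” on all 14 days". It is scored *missing* only when: "Subject reports the reaction as “missing” on all 14 days". Table 3 does the same for any local reaction.
- **Section 3.1.1.2.** Maximum severity is 0 for the same mixture of *no* and *missing*. Otherwise it is the highest grade reported.
- **Section 3.1.2.** Systemic events follow: "The derivations below for systemic events will be handled similarly to the way local reactions are handled".
- **Section 5.3.1.1.** The summary rule takes the 14-day variable as nonmissing "if any day of the 14-day e-diary is available". The section adds that a transmitted day has no missing items, and that the Section 3.1 derivations are the only imputation.

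On completeness, Section 6.6.2.1 describes a table of diary transmission by day, but makes it optional: "The summary may be omitted, as the information is included in reactogenicity listings". The unredacted text sets no minimum number of diary days and gives no sensitivity analysis for partial diaries.

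**The concern.** Local reactions and systemic events within 14 days after Vaccination 1 are primary endpoints (Section 3.1). Scoring an untransmitted day as *no* is single imputation of the favourable value. Because items cannot be skipped on a transmitted day, missingness is by whole day, and a lost day loses every reaction on it.

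The published n and N cannot reveal the effect. A subject with one diary day enters N exactly as a subject with fourteen does.

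The rates are reported by vaccine group and age stratum, where numbers are small. Under Section 7, the interim analyses include all available tolerability data and support choices of dose and formulation. A shortfall that differed between formulations would bear on those choices.

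**Working it through.** **No SAP figure to reproduce.** The SAP states no expected reaction rate and no diary completion rate. The rates and the numbers of incomplete diaries below are assumptions. Only the group sizes come from the SAP.

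**Step 1: direction.** The Table 2 rule applied to test diaries gives:
- one *no* and 13 missing days: scored *no*, whichever day was sent;
- 14 missing days: scored *missing*;
- one *yes* with any number of missing days: scored *yes*.

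A gap can hide a *yes* but cannot create one. Among subjects in N, the reported rate is at or below the rate that complete diaries would give. The highest grade is likewise taken over transmitted days only, so it can also only be lowered.

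**Step 2: group size (Section 2.2).**
- Expanded cohort: 1014 subjects / 13 groups / 2 age groups = 39. One misclassified subject moves a rate by 1/39 = 2.6 points.
- Sentinel cohort: 168 / 2 age groups / 3 dose levels = 28, split 3:3:1 into 12, 12 and 4. In a vaccine group of 12, one subject is 1/12 = 8.3 points.

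**Step 3: size.** Let p be the true rate, m the number of the 39 subjects who lose the early days, and q the chance that such a subject's reaction is missed entirely. Then

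reported rate = p × (1 − q × m/39).

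| p | q | m = 2 | m = 4 | m = 6 |
|---|---|---|---|---|
| 50% | 1 (worst case) | 47.4% | 44.9% | 42.3% |
| 50% | 0.5 | 48.7% | 47.4% | 46.2% |
| 70% | 1 (worst case) | 66.4% | 62.8% | 59.2% |
| 70% | 0.5 | 68.2% | 66.4% | 64.6% |

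Example: 0.5 × (1 − 6/39) = 0.5 × 33/39 = 42.3%. Setting q = 1 means that no affected reactor reports a reaction on any transmitted day. One later *yes* would restore the correct score.

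**Step 4: scattered gaps.** If 6 of 39 subjects each miss one random day, a one-day reaction is hidden with chance 1/14. The loss at p = 50% is 0.5 × 6/39 × 1/14 = 0.5 points, and a reaction of two or more days is never hidden. If instead every subject misses each day with probability 10%, a reaction of 1, 2 or 3 days is wholly missed 10%, 1% or 0.1% of the time. At p = 50% the loss is 5, 0.5 or 0.05 points. Random gaps therefore matter little unless they are frequent and reactions last one day.

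**Step 5: scale.** With 20 reactors of 39 the rate is 51.3% (Clopper-Pearson 95% CI 34.8% to 67.6%). With 4 of them lost it is 41.0% (25.6% to 57.9%). The worst-case loss at p = 50% and m = 6 (7.7 points) is about half the interval's half-width of 16.4 points. The interval does not allow for it.

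**Step 6: choice of sensitivity denominator.** Take 39 subjects, a true 50%, and 6 subjects with a harmless gap that hides no reaction.
- Keeping every reactor but dropping non-reactors with a gap gives 19.5/(39 − 3) = 54.2%, biased upwards.
- Dropping all 6, reactors or not, gives 16.5/33 = 50%.

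The completeness rule must apply to everyone.

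**The case against.** The strongest reply is that the loss is largely visible already. Table 5 (Section 3.1.1.5) codes severe local reactions separately for each day and sets a day to *missing* when all three reactions are missing. Sections 6.1.1.2 and 6.1.2.2 then require n and N for severe local reactions and severe systemic events on each day, by vaccine group and age stratum. If missing days are left out of N, as the coding implies, the daily N is close to a count of diaries transmitted that day. Section 6.6.2.1 also keeps the information in listings. This stands. A reader might infer from the optional completion table that the problem would go unseen, and the SAP does not support that. The daily N does not, however, show how many subjects scored *no* for the whole 14 days had gaps. That link would have to be rebuilt from listings.

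A reader might also infer that the rates are in fact understated, or that the sickest subjects skip early diaries and so distort group comparisons. The SAP gives no completion rate and no evidence of such skipping, and the study is observer-blind. Neither inference is supported.

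Finally, the rule is explicit and consistent, the study is descriptive, and follow-up of missed diary days may be handled in the protocol, which is not at hand. All of this is fair. It supports keeping the main definition, but it does not replace a check on a one-directional imputation in a primary endpoint.

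**Conclusion.** The point holds as a risk of understatement, not as a demonstrated bias. One *no* day out of 14 is enough to count as reaction-free, any error from missing days among counted subjects favours tolerability, and the unredacted text plans no sensitivity analysis.

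The amount cannot be determined from the SAP. With 2 to 6 of 39 subjects losing the early days, a true 50% falls by 2.6 to 7.7 points at worst and by half that if half of their reactions are still seen. With the same number of scattered single-day gaps, the loss is about half a point or less. The upper figures rest on two assumptions: that this many subjects lose the early days, and that none of them reports a reaction later. The change is worth making because it is cheap. The main analysis does not need replacing.

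**What to change.** Keep Tables 2 and 3 and the maximum-severity rule for the main analysis, and add two items to Sections 6.1.1 and 6.1.2.

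1. **One sensitivity table per endpoint** (any reaction or event, and maximum severity), by vaccine group and age stratum, limited to subjects with diaries transmitted on all of Days 1-7. Apply the restriction alike to reactors and non-reactors (Step 6).
2. **In the main table, the number of subjects scored *no* whose Day 1-7 diary was incomplete.** Adding them all to the numerator shows the most that gaps in Days 1-7 could have hidden.

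Both use data already collected. The cost is a little more programming and a slightly smaller N in the sensitivity table. That table is a complete-diary summary and not a bound: it could itself be biased if completeness depends on having a reaction, and it does not cover gaps after Day 7.

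Making the Section 6.6.2.1 completion table mandatory would be convenient, but it adds little beyond the daily N in the severe-reaction tables.
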